6.8. Concomitant Therapy

Any medication (including over-the-counter or prescription medicines, recreational drugs, vitamins, and/or herbal supplements) that the participant is receiving at the time of enrolment or receives during the study must be recorded along with:

- reason for use
- dates of administration including start and end dates
- dosage information including dose and frequency

The Medical Monitor should be contacted if there are any questions regarding concomitant or prior therapy.

Participants must abstain from taking prescription or non-prescription drugs (including NSAIDs, vitamins, recreational drugs, and dietary or herbal supplements) within 7 days (or 14 days if the drug is a potential enzyme inducer) or 5 half-lives (whichever is longer) before the start of study intervention until completion of the final follow-up visit, unless,

in the opinion of the Investigator and Sponsor, the medication will not interfere with the study.

Participants must not currently take any of the following: oral or systemic steroids or any other immune modulators (the washout period will be determined on a case by case basis, in consultation with the GSK medical monitor).

Live vaccination is not permitted within 30 days of dosing or during the study. All other vaccinations (including a two-dose SARS-CoV-2 vaccination and seasonal influenza vaccination as per eligibility requirements) will be completed at least 30 days prior to dosing.

Participants who have not received a MHRA-approved seasonal influenza vaccination will be required to receive vaccination as part of screening if dosing in between 1st October and 30th April. Information on influenza vaccination will be included within the ICF and participants will be provided with the product's Patient Information Sheet prior to vaccination. The period for which influenza vaccination is required for study enrolment will be kept under review and may be changed based on emerging data. Any changes to the vaccination period will be approved by the DEC and will not constitute a protocol deviation or amendment. The influenza vaccination is not considered an Investigational Medicinal Product within this study.

No participants who have a medical history of severe adverse reaction to vaccines will be offered or advised to undergo vaccination to meet the eligibility requirements of this study.

[figure not shown]
Paracetamol, at doses of ≤ 4 grams/day, is permitted for use any time during the study. Other concomitant medication may be considered on a case-by-case basis by the Investigator in consultation with the Medical Monitor.

7. DISCONTINUATION OF STUDY INTERVENTION AND PARTICIPANT DISCONTINUATION/WITHDRAWAL

7.1. Discontinuation of Study Intervention

This is a single-dose study. In rare instances, a participant may not be able to complete the IV infusion or SC injection(s). In such circumstances, if the study intervention is permanently discontinued, the participant will be encouraged to remain in the study for the planned duration, or minimally to complete safety and PK assessments up to Day CCI. The duration for which a participant will be encouraged to remain in the study will be at the discretion of the Investigator in discussion with the Medical Monitor. See the SoA for data to be collected at the time of discontinuation of study intervention and follow-up and for any further evaluations that need to be completed.

CCI

7.2. Study Stopping Criteria

7.2.1. Liver Chemistry Criteria

Liver chemistry stopping, and participant increased monitoring criteria have been designed to assure participant safety and evaluate liver event etiology.

- Any participant meeting the liver chemistry criteria ($ALT \geq 3x ULN$) will have enhanced monitoring as detailed in Section 10.5. The participant should continue in the study, given this is a single dose study.
- Liver events characterized by an $ALT \geq 3x ULN$ but not meeting SAE criteria, if reasonably attributable to GSK3888130B, will result in review by the GSK DEC before further participants are dosed.

7.2.2. QTc Criteria

QTc study stopping criteria, and individual participant increased monitoring criteria, have been designed to assure participant safety. The same QT correction formula must be used for each individual participant to determine eligibility for and discontinuation from the study. Use of Fridericia's formula (QTcF) is preferred in this study. The formula may not be changed or substituted once the participant has been enrolled; for example, if a participant is eligible for the protocol based on QTcF, then QTcF must be used for discontinuation of this individual participant as well. Safety ECGs and other non-protocol specified ECGs are an exception.

Participants that meet either of the bulleted criterion below, additional monitoring will be undertaken until the QTc value is no longer clinically significant. The frequency of this monitoring and the decision as to when the QTc value is no longer clinically significant will be at the discretion of the Investigator. The participant should continue in the study, given this is a single dose study.

- QTcF >500 msec.
- Change from baseline: QTc >60 msec.

If a single ECG demonstrates a prolonged QTc interval, then a further two ECG readings should be obtained over a brief recording period (e.g., 5-10 minute) and the averaged QTc interval used to determine whether the participant meets the criteria to trigger further monitoring.

If a participant meets any of the criteria above, this will result in review by the GSK DEC before further participants are dosed.

7.2.3. SARS-CoV-2 Related Stopping Criteria

- Participants who report symptoms suggestive of SARS-CoV-2 while in the research unit should be isolated in the unit or at home and tested for SARS-CoV-2 infection using an approved molecular test according to local site procedures.
- Participants testing positive for SARS-CoV-2 will be actively followed up, with early referral as per standard of care if there is evidence of deterioration.
- Withdrawal of participants from the study will be at the discretion of the Principal Investigator or designee but should first be discussed and agreed with the GSK Medical Monitor.
- Further study related procedures for the participant, except those required for participant safety and well-being, should be paused until the discussion is complete.
- Participants who test positive for SARS-CoV-2 infection during the course of the study may be replaced at the discretion of the Sponsor and in consultation with the Principal Investigator.

7.2.4. Pharmacokinetic Dose Adjustment / Stopping Criteria

All available PK data from previous dose levels will be rapidly evaluated to estimate and predict the systemic exposure (Cmax and AUC(0-∞)) to the next dose level.

The PK stopping criteria will be mean exposure exceeding or predicted to exceed AUC(0-∞) of **CCI** μg·mL⁻¹·h or Cmax of **CCI** μg/mL, which are **CCI** of the exposure observed at NOAEL in the 4-week monkey toxicity study.

If the PK stopping criteria is met, then dose escalation will be stopped or dose adjustment will be planned, as appropriate.

7.2.5. Safety Dose Adjustment / Stopping Criteria

The GSK DEC will temporarily halt the study based on the following:

- $CD4^+$ T cell counts below $0.2 \times 10^9/L$ are considered clinically relevant (BHIVA Guidelines Subcommittee, National Cancer Institute - Common Terminology Criteria for Adverse Events (Version 5, NCI-CTCAE) grade 3 or greater) and if sustained for at least 7 days in one participant, this will result in review by the GSK DEC before further participants are dosed.
- **CCI** [REDACTED]
[REDACTED]
[REDACTED]
this will result in review by the GSK DEC before further participants are dosed.
NOTE: **CCI** [REDACTED]
[REDACTED] which, in the opinion of the Investigator, can be reasonably attributed to GSK3888130B.
- **CCI** [REDACTED] are considered clinically relevant (National Cancer Institute - Common Terminology Criteria for Adverse Events (Version 5, NCI-CTCAE) grade 3 or greater). If the **CCI** [REDACTED] in the opinion of the Investigator, can be reasonably attributed to GSK3888130B then this will result in review by the GSK DEC before further participants are dosed.
- Clinically significant [National Cancer Institute - Common Terminology Criteria for Adverse Events (Version 5, NCI-CTCAE) grade 3 or greater] infusion reactions occurring in one participant.
- As a result of review of safety data at the end of each cohort.
- If one or more participants from any dose level experiences a Serious Adverse Event (SAE) which has a reasonable possibility of relation to GSK3888130B, no further participants will be dosed until a full safety review of the data has taken place.
- If two or more participants in the same cohort experience a 'severe' non-serious adverse reactions which has a reasonable possibility of relation to GSK3888130B, no further participants will be dosed until a full safety review of the data has taken place. 'Severe' non-serious adverse reactions can be either within or not within the same system organ class.

In the event of reaching the stopping criteria, the dose escalation will stop, and no further participants will be dosed. If after consultation the Sponsor deems that dosing can resume at that level or higher the Sponsor will submit an application for a substantial amendment to the Regulatory Agency to present the data and approve a revision to the protocol.

The above criteria will apply even if measured PK parameters are below the pre-specified PK stopping criteria. Every effort will be made to take a blood sample for PK analysis at the time of any of the above events.

7.3. Participant Discontinuation/Withdrawal from the Study

- A participant may withdraw from the study at any time at his/her own request or may be withdrawn at any time at the discretion of the Investigator for safety, behavioural, or compliance reasons. This is expected to be uncommon.
- At the time of discontinuing from the study, if possible, an early discontinuation visit should be conducted, as shown in the SoA. See SoA for data to be collected at the time of study discontinuation and follow-up and for any further evaluations that need to be completed. The participant will be permanently discontinued from the study at that time.
- If the participant withdraws consent for disclosure of future information, the sponsor may retain and continue to use any data collected before such a withdrawal of consent.
- If a participant withdraws from the study, he/she may request destruction of any samples taken and not tested, and the Investigator must document this in the site study records.

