Viral serology (HIV, hepatitis B and C)	X					Hepatitis B screening to include surface antigen and core antibody test. Viral serology does not need to be repeated for rescreens if within 3 months of initial screening.
TB screening (QuantiFERON Gold)	X					TB screening does not need to be repeated for rescreens if within 3 months of initial screening.
12-lead ECG	X		X			Performed in triplicate.

Procedure	Screening (up to 28 days before Day 1) ¹	Day -1		E.D	Follow-up (CCI [REDACTED] days post last study visit)	Follow-up (CCI [REDACTED] days post last study visit)	Notes E.D = early discontinuation/withdrawal 1. In participants who require an influenza vaccination and/or SARS-CoV-2 booster, the screening window may be increased to 60 days. This extended screening window applies only to those participants, and if their initial screening assessments are conducted more than 28 days prior to Day 1, screening assessments will be repeated within 28 days of Day 1.
CCI	[REDACTED]						
Concomitant medication review	X	X	X	X	X	X	
Admission		X					

Procedure	Screening (up to 28 days before Day 1) ¹	Day -1	E.D	Follow-up (CCI [REDACTED] days post last study visit)	Follow-up (CCI [REDACTED] days post last study visit)	Notes E.D = early discontinuation/withdrawal 1. In participants who require an influenza vaccination and/or SARS-CoV-2 booster, the screening window may be increased to 60 days. This extended screening window applies only to those participants, and if their initial screening assessments are conducted more than 28 days prior to Day 1, screening assessments will be repeated within 28 days of Day 1.
Laboratory assessments (include clinical chemistry and haematology panels)	X	X	X			
CD4+ T cell counts	X	X				
Urinalysis (Dipstick ±microscopy)	X	X				If dipstick is positive or participant has urinary symptoms send for microscopy. CCI [REDACTED] [REDACTED].
Vital signs	X	X	X			
Brief Physical exam		X	X			

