Procedure	Screening (up to 28 days before Day 1) ¹	Day -1	E.D	Follow-up (CCI [REDACTED] days post last study visit)	Follow-up (CCI [REDACTED] days post last study visit)	Notes E.D = early discontinuation/withdrawal 1. In participants who require an influenza vaccination and/or SARS-CoV-2 booster, the screening window may be increased to 60 days. This extended screening window applies only to those participants, and if their initial screening assessments are conducted more than 28 days prior to Day 1, screening assessments will be repeated within 28 days of Day 1.
Breath alcohol test, smoking breath test and urine drug screen	X	X				
SARS-CoV-2 Test	<=====>					As per local guidelines.
Confirmation of postmenopausal status in females if required.	X					FSH and oestradiol test.
AE Review			X	X	X	
Blood collection for Immunogenicity testing			X			
SAE Review	X	X	X	X	X	Collected from signing the informed consent form.

Procedure	Screening (up to 28 days before Day 1) ¹	Day -1		Follow-up (CCI days post last study visit)	Follow-up (CCI days post last study visit)	Notes E.D = early discontinuation/withdrawal 1. In participants who require an influenza vaccination and/or SARS-CoV-2 booster, the screening window may be increased to 60 days. This extended screening window applies only to those participants, and if their initial screening assessments are conducted more than 28 days prior to Day 1, screening assessments will be repeated within 28 days of Day 1.
CCI		CCI				

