3. OBJECTIVES AND ENDPOINTS

Objectives	Endpoints
Primary	

 To investigate the safety and tolerability of single IV and SC doses of GSK3888130B in healthy participants. 	
 Occurrence of Adverse Events (AEs) and Serious Adverse Events (SAEs). Occurrence of clinically significant changes in laboratory values (CD4⁺ T cell counts, haematology, chemistry, urinalysis and virology), vital signs and 12-lead electrocardiogram (ECG) readings.
Secondary	

 To characterise the serum PK profile of single IV or single SC doses of GSK3888130B in healthy participants. 	
 Serum concentrations of GSK3888130B and derived PK parameters as data permit, including: area under the concentration-time curve [AUC], maximum concentration [Cmax], time to Cmax [Tmax], half-life [t_{1/2}], clearance [CL].

 To evaluate the immunogenicity of single doses of GSK3888130B in healthy participants. 	
 Incidence of Anti-Drug Antibodies (ADAs) against GSK3888130B.

 To characterise the effects of GSK3888130B on target engagement (TE). 	
 Change from baseline in CCI [REDACTED] [REDACTED] over time.

Objectives	Endpoints

• To characterise the effect of single doses of GSK3888130B on PD biomarker Bcl-2.	
• Change from baseline in T cell Bcl-2, measured in blood over time.

Objectives	Endpoints
CCI	

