8.8. Immunogenicity Assessments

Antibodies to GSK3888130B will be evaluated in serum samples collected from all participants according to the SoA. Additionally, serum samples should also be collected at the final visit from participants who discontinued study intervention or were withdrawn from the study. These samples will be tested by the Sponsor or Sponsor's designee.

Serum samples will be screened for antibodies binding to GSK3888130B and the titer of confirmed positive samples will be reported. Other analyses may be performed to verify the stability of antibodies to GSK3888130B and/or further characterize the immunogenicity of GSK3888130B.

The detection and characterization of antibodies to GSK3888130B will be performed using a validated assay method by or under the supervision of the Sponsor. All samples collected for detection of antibodies to study intervention will also be evaluated for GSK3888130B serum concentration to enable interpretation of the antibody data.

Antibodies may be further characterized and/or evaluated for their ability to neutralize the activity of the study intervention.

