10.2. Appendix 2: Clinical Laboratory Tests

The tests detailed in [Table 1](#) will be performed by the local laboratory.

Protocol-specific requirements for inclusion or exclusion of participants are detailed in [Section 5](#) of the protocol.

Additional tests may be performed at any time during the study as determined necessary by the Investigator or required by local regulations.

Table 1 Protocol-Required Safety Laboratory Tests

Laboratory Assessments	Parameters			
Haematology	Platelet Count	RBC Indices: MCV MCH %Reticulocytes	WBC count with Differential: Neutrophils Lymphocytes Monocytes Eosinophils Basophils	
	RBC Count			
	Haemoglobin			
	Haematocrit			
	CD4 ⁺ T cell Count	CCI [REDACTED]		
Clinical Chemistry ¹	Urea/BUN	Potassium	Aspartate Aminotransferase (AST)/ Serum Glutamic-Oxaloacetic Transaminase (SGOT)	Total and direct bilirubin
	Creatinine	Sodium	Alanine Aminotransferase (ALT)/ Serum Glutamic-Pyruvic Transaminase (SGPT)	Total Protein
	Glucose (non-fasting)	Calcium	Alkaline phosphatase ²	
	CCI [REDACTED] [REDACTED] [REDACTED]	CCI [REDACTED]		
Routine Urinalysis	
 Specific gravity pH, glucose, protein, blood, ketones, bilirubin, urobilinogen, nitrite, leukocyte esterase by dipstick Microscopic examination (if blood or protein is abnormal, or if any other trace is detected) 			

Laboratory Assessments	Parameters
	
 • CCI ██████████ described in SRM
Viral quantification and serology	
 • EBV, CMV and VZV. • SARS-CoV-2 (serology only)
Other Screening Tests	
 i. Follicle-stimulating hormone and oestradiol (as needed in women of non-childbearing potential only) ii. Alcohol and drug screen (to include at minimum: amphetamines, barbiturates, cocaine, opiates, cannabinoids and benzodiazepines) iii. Serology (HIV antibody, hepatitis B surface antigen [HBsAg], hepatitis B core antibody and hepatitis C virus antibody and hepatitis C RNA) iv. Mycobacterium tuberculosis QuantiFERON Gold v. SARS-CoV-2 testing (performed as per site local procedures) vi. Smoking breath test

NOTES:

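### The early discontinuation visit marks no EBV/CMV/VZV sample and no urinalysis, and leaves CD4+ unclear, although all three are in the primary safety endpoint

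*Protocol*

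**What the plan says.** Protocol 7.3 covers participants who leave at their own request and those the investigator withdraws "for safety, behavioural, or compliance reasons. This is expected to be uncommon". For all of them, where possible, "an early discontinuation visit should be conducted, as shown in the SoA". After that visit, "The participant will be permanently discontinued from the study at that time". What the E.D. column marks is therefore the last clinic information the protocol asks for.

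The primary endpoint (Protocol 3, repeated in SAP 1.1) covers AEs, SAEs, vital signs, 12-lead ECG and clinically significant "changes in laboratory values (CD4⁺ T cell counts, haematology, chemistry, urinalysis and virology".

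Three rows in the SoA matter here:

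- **EBV/CMV/VZV.** This row appears only in the dosing-period tables, 1.3.2 (IV) and 1.3.3 (SC), which have no E.D. column. The one printed viral serology row in 1.3.1 is for HIV and hepatitis at screening.
- **CD4+.** The row "CD4+ T cell counts" in 1.3.1 is marked at screening and Day -1 only. Appendix 2, Table 1, however, lists "CD4 ⁺ T cell Count" in its haematology block, and the haematology panel is marked at E.D.
- **Urinalysis.** This is marked at screening and Day -1, not at E.D.

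The plan does secure a closing sample for a secondary endpoint. The row "Blood collection for Immunogenicity testing" is marked at E.D., and Section 8.8 states that "serum samples should also be collected at the final visit from participants who discontinued study intervention or were withdrawn from the study".

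**The concern.** Section 4.2 says the baseline, midpoint and end-of-study viral samples are there to characterise infection risk, asymptomatic infection included. A participant who leaves before the last of these loses it, and the E.D. visit does not replace it. The symptom-triggered sampling in 8.2.8 cannot help someone without symptoms.

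The protocol's own background shows why this matters. In the 12-week anti-IL-7R study summarised in 2.3.1, four participants seroconverted for EBV, two of them with symptoms, and one further participant had asymptomatic CMV DNA. On that account up to (4 - 2) + 1 = 3 of 5 viral findings would not have triggered a symptom-based sample. That study used repeat dosing in patients with type 1 diabetes, so it illustrates the mechanism and gives no rate for this trial.

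For CD4+ the stake is narrower. Section 8.2.5 already calls for a repeat of an abnormal laboratory value seen during participation. What could be missed is a first fall that occurs after the last scheduled count and is present at withdrawal. A site reading the SoA row by row would not draw that count; a site reading Appendix 2 would.

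**Working it through.** The plan gives no figure on this point. The check sets the endpoint components against the schedule.

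**Step 1. Column alignment.** The tables are damaged, so I checked the E.D. position on rows whose meaning is plain. AE review is marked at E.D. and at both follow-up calls; immunogenicity is marked at E.D. only; ECG is marked at screening and E.D. All three place E.D. third among the five named visits, after screening and Day -1.

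**Step 2. Primary-endpoint components at the E.D. visit.**

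| Component | Marked at E.D. in SoA 1.3.1? |
|---|---|
| AEs | Yes |
| SAEs | Yes |
| Haematology | Yes |
| Chemistry | Yes |
| Vital signs | Yes |
| 12-lead ECG | Yes |
| CD4+ count | Own row blank; possibly included through haematology (Appendix 2) |
| Urinalysis | No |
| Virology (EBV/CMV/VZV) | No printed row |

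Six of nine are clearly covered, two are not, and one is ambiguous. Among the five laboratory groups, two are clearly covered (haematology and chemistry).

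**Step 3. Can CD4+ be settled from the documents?** If the laboratory-panel row always included CD4+, a separate CD4+ row would be redundant. As extracted, the two rows follow different schedules in the dosing period: 10 panel marks and 8 CD4+ marks for IV, 10 and 9 for SC. That leans towards CD4+ being separate from the panel. Appendix 2 leans the other way. Unclear is the accurate description.

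**Step 4. Post-dose viral samples for a withdrawing participant.** Three sets are scheduled: baseline, midpoint and end of study. Post-dose that is 3 - 1 = 2. Assume the E.D. visit takes place.

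| Time of withdrawal | Now | With an E.D. sample |
|---|---|---|
| Before the midpoint sample | 0 | 0 + 1 = 1 |
| After midpoint, before end of study | 1 | 1 + 1 = 2 |

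With baseline added, the totals are 1 + 1 = 2 and 1 + 2 = 3, never more than the 3 a completer gives.

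**Step 5. Do other provisions supply the sample?** Section 8.2.8 requires symptoms. Section 8 permits unscheduled samples for safety reasons but does not require them. The SoA notes allow additional visits, again as an option. None secures a closing viral sample from a symptom-free participant who leaves.

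**The case against.** The strongest case is that this is a small gap seen through a damaged table. SoA 1.3.1 has fully redacted rows, and its concomitant-medication row shows more marks than there are named visits. The E.D. visit already has AE and SAE review, examination, vital signs, ECG and safety laboratory tests. It is held only if possible, and 7.4 treats unreachable participants as withdrawn, so some will have no visit at all. An E.D. viral sample is also neither a midpoint nor an end-of-study sample, and the visible SAP gives it no place.

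Most of this stands and limits the size of the point. It does not remove it. The EBV/CMV/VZV row is printed openly in 1.3.2 and 1.3.3, so redaction is an unlikely reason for its absence from 1.3.1, although this cannot be excluded.

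Three stronger readings are tempting, and the documents do not support them:

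- **CD4+ is not measured at E.D.** Appendix 2 allows the opposite reading, so the need is for clarification.
- **A share of a cohort's safety information is lost and could be recovered.** An E.D. sample records status at withdrawal. It recovers nothing that happens later, so fractions of a cohort or upper limits on late event rates do not measure what this change would gain.
- **Section 7.2.3 is deficient because it lacks the stay-in-study sentence used for liver and QTc events.** That section already requires active follow-up of participants who test positive and Medical Monitor agreement before withdrawal. Isolation is a fair reason for case-by-case judgement.

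**Conclusion.** The point holds as a cheap, minor improvement. The E.D. visit shows no EBV/CMV/VZV sample and no urinalysis, and leaves CD4+ to interpretation, although all three are in the primary safety endpoint. The firmest part is virology: a symptom-free participant who withdraws before the end-of-study visit has no closing viral sample, contrary to the purpose stated in 4.2. The gain is one post-dose viral set per such participant.

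This rests on the printed SoA rows being complete for these tests and on the E.D. visit taking place. The documents give no withdrawal rate; 7.3 expects withdrawal to be uncommon. Confidence is medium because of the redactions and the state of the extracted table.

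**What to change.** In the E.D. column of SoA 1.3.1, mark EBV/CMV/VZV serology and viral quantification, CD4+ count and urinalysis. Add a note that these are not needed where the end-of-study sample has already been taken, for example when someone leaves between the last clinic visit and the final telephone call. It would help to state in the SAP how E.D. viral results are reported, for instance as a separate time point or in a listing. Sections 7.2.3 and 7.3 need no change.

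The assays are already run in the study and blood is already drawn at the E.D. visit. The burden is one extra sample set per withdrawal. The change belongs in a protocol amendment, which under 10.1.1 needs ethics approval before implementation, so it is best bundled with the next one.
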